The proposed study has been designed as part of a program of research sponsored by the USA-based non-profit research and educational organization, the Multidisciplinary Association for Psychedelic Studies (MAPS), with the long-term goal of developing MDMA into a prescription medication with US Food and Drug Administration (FDA) and European Medicines Agency (EMEA) approval. MAPS is currently sponsoring an ongoing study of MDMA-assisted therapy in patients with PTSD taking place in Charleston, South Carolina, in which 11 out of 20 subjects have already completed the protocol. MAPS is also in the protocol design and approval phase for two studies of MDMA-assisted therapy in patients with PTSD, to be conducted in Madrid, Spain, under the direction of [name]. candidate, and in Tel Aviv, Israel, under the direction of [name], Department of Psychiatry, Tel Aviv University. MAPS is also sponsoring an FDA-approved study to take place at Harvard Medical School's McLean Hospital that will investigate MDMA-assisted psychotherapy in people with anxiety related to advanced stage cancer.

MDMA is a ring-substituted phenylisopropylamine derivative invented by the Merck pharmaceutical company in 1912 that bears structural and pharmacological similarities to both the stimulant amphetamine and the psychedelic drug mescaline. It was initially patented by Merck as an intermediary product and then rediscovered by chemist Alexander Shulgin in the 1970s. In the United States, MDMA was used as an adjunct to psychotherapy by a considerable number of psychiatrists and other therapists before it was made a Schedule 1 (Betäubungsmittel) drug in 1985 as a result of extensive non-medical use (Greer and Tolbert 1986; Saunders 1993; Stolaroff 2004). Prior to scheduling, MDMA in combination with psychotherapy was used in the treatment of neuroses, relationship problems and PTSD (Adamson 1985; Greer and Tolbert 1998; Metzner and Adamson 2001; d'Otolora, 2004). Case reports and narrative accounts of MDMA-assisted therapy indicate that the treatment was often successful. Based on these experiences, assertions have been made that MDMA, used in the proper therapeutic setting, can act in several beneficial ways. Specifically, MDMA can “reduce or somehow eliminate fear of a perceived threat to one’s emotional integrity” (Greer and Tolbert 1998). Elimination of these “conditioned fear responses” can lead to more open and comfortable communication about past traumatic events, greater access to information about them, and a more accurate perspective about their significance in the present. Some clinicians and researchers have asserted that MDMA causes increased empathy or compassion for self and others, decreased defensiveness and strengthening of the therapeutic alliance, and that the above factors taken together can provide the opportunity for a corrective emotional experience (Greer and Tolbert, 1998, Holland, 2001). Some investigators suggest that MDMA be categorized as part of a new class of psychotropic agents referred to as entactogens (Nichols and Oberlander, 1990). The term refers to MDMA and similar substances that produce increased sensitivity to emotions, increased insights about the self, especially in the context of interpersonal relationships, and increased feelings of closeness to others.

MDMA was made illegal in the US and Switzerland shortly after a rise in use of MDMA outside the confines of psychotherapy. Ecstasy (material represented as MDMA) continues to be used throughout the world. Serious adverse events such as hyperthermia, hyponatremia or liver damage have occurred in association with ecstasy use, but these are relatively rare given the widespread use of ecstasy. It is notable that the purity and potency of illicit ecstasy is often unknown, but that recent surveys of ecstasy tablets indicate that up to 40% of tablets are adulterated or contain no MDMA (Cole et al. 2002; Baggott et al. 2000). There is evidence that the use of frequent, high doses of MDMA in uncontrolled settings exacerbates its risks. The majority of serious adverse events after Ecstasy consumption have occurred in conditions of high ambient temperature, long periods of strenuous activity (dancing) and insufficient or uncontrolled fluid intake. All of these environmental

circumstances may enhance or exacerbate problematic effects of MDMA. By contrast, people taking part in MDMA-assisted therapy do not experience any of these behavioral or environmental factors.

Initial human trials of MDMA demonstrated that the drug can be administered safely under controlled conditions, and no drug-related serious adverse events have been reported during the course of the ongoing Phase II study in the US. Preliminary examination of this data has found no deterioration in condition after MDMA-assisted psychotherapy. When the blind was broken for the first 15 subjects, it was found that people receiving MDMA demonstrated greater improvement than people receiving placebo (Mithoefer 2007), and preliminary analyses did not indicate any effects of MDMA on memory. After reviewing data from the last 15 subjects, the Data Safety Monitoring Board (DSMB) recommended that the study continue without any modifications.

This study of MDMA-assisted therapy will be the first Phase II study to take place in Switzerland examining MDMA-assisted psychotherapy as a potential treatment for people with treatment resistant PTSD. If data from MAPS' pilot studies continue to produce promising results, then MAPS will use the information gathered from these studies to formulate two large (N = approximately 280) multi-site Phase III studies of MDMA-assisted psychotherapy, one to be conducted throughout the United States and one to be conducted throughout Europe and Israel. MAPS' Clinical Plan (Doblin 2002) estimates that this process will require at least five years and will involve at least 600 subjects.

2. The Protocol

2.1. Summary of the Proposed Study

This protocol is for a randomized, double-blind, active placebo controlled study of the safety and efficacy of 3,4-methylenedioxymethamphetamine MDMA-assisted psychotherapy in patients with treatment-resistant posttraumatic stress disorder (PTSD). In this study, 12 patients will receive either an active placebo dose or a fully active dose of MDMA during three experimental psychotherapy sessions, each six to eight hours long, scheduled three to five weeks apart. Participants assigned to receive the active placebo and participants assigned to receive the fully active dose will receive the same course of psychotherapy, which consists of two introductory sessions prior to the first experimental (active placebo or fully active dose MDMA) session, follow-up psychotherapy sessions occurring a day after each experimental session, and two to four integrative psychotherapy sessions conducted on a weekly basis after each experimental session, with the first of these sessions scheduled a week after each experimental session. Active placebo will be 25 mg MDMA followed two and a half hours later by 12.5 mg, and the fully active dose will be 125 mg followed two and a half hours later by 62.5 mg. Extent of PTSD symptoms will be assessed by an independent rater at baseline, 3 weeks after the second and third experimental session and two, six and 12 months after the third MDMA-assisted session. The Clinician Administered PTSD Scale (CAPS) will serve as the primary outcome measure. We hypothesize that PTSD symptoms will be reduced in participants receiving the fully active dose of MDMA, that MDMA-assisted psychotherapy will be well-tolerated and will not produce serious adverse effects in this population, that three experimental sessions will lead to better results than two sessions, and that results are stable at the follow up assessments at 2, 6 and 12 months after the last experimental session.

Participants assigned to the active placebo condition will be given the opportunity to take part in an open-label continuation of the study with fully active doses of MDMA, referred to here as "Stage 2". This opportunity will be offered immediately after the end of treatment outcome measures are completed 3 weeks after the third experimental session, with the blind to be broken by a research assistant not connected with the study in any other way. Data gathered 3 weeks after the third experimental session will be treated as the baseline for Stage 2, and outcome measures will be administered 3 weeks after the second and third experimental session and 2, 6, and 12 months after the

third MDMA session for all people who consent to take part in Stage 2, which will be structured in an identical manner to Stage 1.

Based on the reviewed research, it is very unlikely that the doses we propose to administer in a controlled clinical setting will cause memory impairment or other neurological or physiological damage. These low risks are more than balanced by the potential benefits to the volunteers. All participants must have had at least one unsuccessful attempt at treatment with medications and/or psychotherapy, and they may find some relief associated either with MDMA-assisted psychotherapy or with the non-drug psychotherapy to be administered to the control subjects.

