2.6. Questions and Hypotheses

The following main questions are to be explored in the proposed study:

1. Can MDMA, in the doses to be used in this study, be safely administered in the population of treatment-resistant PTSD patients without any serious adverse events?
2. Will patients receiving the larger, fully active dose of MDMA, in combination with non-drug assisted psychotherapy, demonstrate greater symptomatic improvement than patients given an active placebo dose of MDMA in combination with non-drug psychotherapy?
3. Will patients receiving three MDMA sessions in combination with non-drug psychotherapy demonstrate an additional improvement compared to patients receiving only two sessions?
4. Can treatment effects of MDMA-assisted psychotherapy be maintained beyond end of treatment?

Based on the reviewed research, the following hypotheses were formulated:

Re 1. PTSD patients receiving the fully active dose of MDMA will not experience any serious adverse events. The supplemental dose of MDMA will be tolerated both in the low and fully active dose conditions.

Re 2. There will be trends for people receiving the fully-active dose of MDMA to demonstrate greater symptomatic improvement after receiving MDMA-assisted therapy than people receiving the low dose of MDMA, including greater reduction in symptom severity and intensity, and overall improvement in PTSD symptoms, as measured via the CAPS and PDS, with CAPS score serving as the primary outcome measure.

Re 3. 3 experimental MDMA-assisted sessions will lead to better results compared to only 2 experimental MDMA-assisted sessions, as measured via the CAPS and PDS, with CAPS score serving as the primary outcome measure.

Re 4. The treatment gains will remain stable at the 2, 6 and 12 months assessments.

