2.8. Methods

2.8.1. Drugs and Dosage

Upon enrollment in the study, the participant will be randomly assigned to the Low Dose or the Fully Active Dose condition. Condition assignment will be performed with a table of random numbers generated by the Institute for Statistics, University of Bern. All study investigators will remain blind to condition assignment. If there is an adverse event or other emergency requiring knowledge of participant's condition assignment, the blind may be broken for an individual participant.

Participants in the Low Dose condition are assigned to receive an initial dose of 25 mg MDMA followed 2.5 hours later by a supplemental dose of 12.5 mg MDMA. Participants assigned to the Fully Active dose condition will receive an initial dose of 125 mg followed 2.5 hours later by a supplemental dose of 62.5 mg MDMA. Eight of 12 subjects, or 66.6%, will be assigned to the Fully Active dose condition, and 4 of 12, or 33.3%, will be assigned to the Low Dose condition.

The two doses of MDMA chosen for the Low Dose condition have been selected on the basis of their ability to produce minimal but detectable subjective effects (Grob et al. unpublished; Harris et al. 2002) and thus serve as an active placebo. The cumulative dose of 37.5 mg MDMA is not expected to produce a significant reduction in anxiety or a significant increase in access to emotionally upsetting material, though this dose may produce slight alterations in consciousness, such as increased relaxation or tension (Harris et al. 2002). The initial 125 mg dose of MDMA selected for the Fully Active Dose condition was chosen on the basis of case reports of MDMA-assisted psychotherapy conducted in the US prior to scheduling (Greer and Tolbert 1986), as well as on data obtained from [name] MAPS-sponsored MDMA/PTSD pilot study currently underway in the United States. This dose is expected to reduce fear in response to emotionally upsetting thoughts, feelings or memories and to increase access to emotionally intense material, and is thus expected to be therapeutically active. Doses equal to or exceeding 125 mg have been employed in previous uncontrolled and controlled studies of MDMA (Cami et al. 2000; Grob et al. 1996; Grob et al. Unpublished; Harris et al. 2002; Lester et al. 2000; Mas et al. 1999; Styk 2007; Tancer et al. 2001; Tancer et al. 2003; Vollenweider et al. 1998).

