With participants carefully monitored for any indicators of adverse events, the initial doses of either 125 mg or 150 mg, and the cumulative dose of 187.5 mg or 225 mg respectively will prove to be tolerable and pose no more than minimal risk. The side effect profile is expected to increase with the higher dose but it is considered unlikely that there will be any Serious Adverse Events (SAEs) or any persisting side effects.

Table 1. Dose Regimen

	Initial Dose	Supplemental Dose	Cumulative Dose
Low Dose	25 mg	12.5 mg	37.5 mg
Fully Active Dose	125 mg	62.5 mg	187.5 mg
20% Larger Active Dose	150 mg	75 mg	225 mg

Supplemental doses for both the Low and the Fully Active dose conditions were chosen to be half the size of initial doses, and the dosage and schedule of dosing was chosen on the basis of case reports describing the use of MDMA in psychotherapy (Greer and Tolbert 1998; Stolaroff 2004, Styk 2007). Supplemental dosing performed 2.5 hours after the initial dose is expected to extend the course of drug effects without increasing their intensity. Both the Low and Fully Active dose conditions use supplemental doses that are half of the initial dose, to make dosing schedule equivalent across the conditions.

Participants will receive an initial dose of MDMA approximately 1 to 1.5 hours after they arrive at [name] office for each experimental session. If the investigators believe the participant is able to tolerate a supplemental dose and the participant agrees to take it, then a supplemental dose will be offered 2.5 hours later. The investigators will not administer the supplemental dose if the participant is exhibiting signs or symptoms that would place him or her at greater risk of experiencing a serious adverse event.

Each dose will consist of the specified amount of racemic MDMA mixed with an inactive substance, such as lactose, to prevent the investigators from distinguishing doses through weight or appearance of the capsules. Initial doses will be distinguished from supplemental doses through labeling them "Dose 1" and "Dose 2" or "first" and "second" dose to ensure that the correct dose is administered at the scheduled time. Each dose of MDMA will be administered along with 250 to 300 mL electrolyte-containing fluid. MDMA will be administered during each of the three experimental sessions, with the second and third session scheduled to fall two to four weeks after the previous experimental session.

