2.8.6. Open Label Continuation for Active Placebo Patients ("Stage 2")

After each participant completes all outcome measures on the session scheduled 3 weeks after the third experimental session (T2), the participant will have a 30-minute meeting with the principal investigator. During this meeting, the blind will be broken for the individual participant while retaining the blind for the independent assessor. If a participant had received the Low (25 mg followed 2.5 hours later by 12.5 mg) dose of MDMA during the course of the study, she or he would be offered an opportunity to enroll in the open label continuation of the study, referred to as Stage 2. He or she would give written informed consent to take part in this second stage of the study, with consent given separately from the initial consent. If the participant consents to take part in Stage 2 of the study, he or she would receive the Fully Active dose of MDMA (125 mg followed 2.5 hours later by 62.5 mg) during three experimental sessions scheduled two to four weeks apart. Outcome measures administered three weeks after the third experimental session will serve as baseline measures for Stage 2. The participant would undergo one preparatory non-drug psychotherapy session 1 to 2 weeks prior to the first experimental session, and he or she would receive non-drug psychotherapy follow-up sessions according to the same schedule described for the active placebo controlled study. Procedures for non-drug psychotherapy sessions, experimental sessions, weekly telephone contact and outcome measure administration will be the same as those employed in the first stage of the study.

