3.3 Safety Objectives

The safety objective presented in the protocol is item 1 in the Study Objectives listed above and has been formulated as individual objectives below:

- To assess blood pressure and pulse during experimental sessions using automated blood pressure and pulse monitoring equipment.
- To assess body temperature at regular intervals during experimental sessions.
- To assess experience of degree of psychological distress by repeated administration of the Subjective Units of Distress (SUD) during experimental sessions.

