Population: All enrolled, intention to treat, per protocol, partial crossover, Extended Assessment 2

Data included: Per each AE; Subject number, Patient identifier

- Age, race, sex, weight (height, if relevant)
- Location of CRFs, if provided
- Adverse event description (preferred term, reported term)
- Duration of the adverse event
- Severity (e.g., mild, moderate, severe)
- Seriousness (serious/non-serious)
- Action taken (none, dose reduced, treatment stopped, specific treatment instituted etc.)
- Outcome (e.g., CIOMS format)
- Relatedness process of determination given if possible
- Date of onset or date of clinic visit at which the event was discovered
- Timing of onset of the adverse event in relation to last dose of investigational product (if or when applicable)
- Investigational product dose in absolute amount, mg/kg
- Duration of investigational product treatment (Stage 1, Stage 2, Stage 3)
- Concomitant treatment during study.

Format of presentation: All adverse events for each patient, including the same event on several occasions will be listed, giving both preferred term and the original term used by the investigator. The listing should be by treatment group and will include:

Analysis #1

Goal: To see if one or more demographic factor and condition alter the number and severity of adverse events and spontaneously reported reactions collected across the course of the study.

Population: All enrolled, intention to treat, per protocol, partial crossover, Extended assessment 1, Extended assessment 2

Data included: Number of AEs collected across Stage 1, Stage 2 and Stage 3, and any AEs collected before 2, 6 and 12 month follow up for Extended Assessment 1 participants, Number of severe AEs collected across Stage 1, Stage 2 and Stage 3 (when applicable), average severity rating of AEs occurring during the study, number of individual spontaneously reported reactions and average severity of self-reported reactions.

Format of analysis: Two-way ANOVA for gender, linear regression analysis for age

Between-groups factors: Condition (125 mg MDMA, 25 mg MDMA, 150 mg MDMA (when applicable)); gender; age

Analysis #2

Goal: to see if there is an effect of presence versus absence of supplemental dose upon number of AEs and spontaneously reported reactions and number of severe AEs and spontaneously reported reactions.

Population: All enrolled, intention to treat, per protocol, partial crossover, extended assessment 2

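### The trial's first question, on serious adverse events, is worded causally in one place and as any-cause in another, and no proportion or interval is planned to answer it

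*Protocol*

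**What the plan says.** The first study question is about serious adverse events, and the documents put it in several ways.

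- Protocol 2.1 hypothesises that "MDMA-assisted psychotherapy will be well-tolerated and will not produce serious adverse effects in this population".
- Protocol 2.6, Question 1, asks whether MDMA at the study doses can "be safely administered in the population of treatment-resistant PTSD patients without any serious adverse events". SAP 3.0 repeats this question unchanged.
- Protocol 2.6, Re 1, gives the matching hypothesis: "PTSD patients receiving the fully active dose of MDMA will not experience any serious adverse events".
- Protocol 2.8.1 is milder: "it is considered unlikely that there will be any Serious Adverse Events (SAEs) or any persisting side effects".
- SAP 3.3 says: "The safety objective presented in the protocol is item 1 in the Study Objectives listed above and has been formulated as individual objectives below". Three objectives follow: blood pressure and pulse, body temperature, and the Subjective Units of Distress (SUD) rating. None mentions serious events.

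On reporting, SAP 5.2 counts adverse events among the safety measures, and SAP 6.5 tabulates them by condition and by relatedness. SAP 6.5.3 records seriousness (yes or no) and three levels of relatedness, and lists each event with its dose, timing and outcome. Protocol 2.8.3 covers only the CAPS and PDS. The adverse-event analyses in SAP 6.5.3 are ANOVA and regression on event counts and severity. No section plans the proportion of participants with a serious event, or an interval for it.

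**The concern.** Two things are unsettled. The first is what counts. The 2.1 wording is causal and the Re 1 wording is not, so the same data can agree with one and contradict the other. The protocol elsewhere keeps the two ideas apart: its introductory statement reports no drug-related serious events in the ongoing US study, while 2.2.2 reports no serious events of any kind in the Phase I trials.

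The second is how a result is to be read. Both hypotheses are absolute, and the only planned output on serious events is a set of tables and a listing. If no serious event occurs, nothing in the plan stops the report from saying that the hypothesis was borne out, and nothing tells the reader how large a risk the data still allow. The introductory statement says that the pilot results will be used to design two Phase III studies of about 280 people each, so the precision of the safety result has a practical use.

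**Working it through.** The documents give no safety sample-size, power or precision figure, so there is nothing of that kind to reproduce.

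**Step 1: one unrelated serious event in a full-dose participant, set against each statement.**

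| Statement | Cause | Group | Contradicted? |
|---|---|---|---|
| Protocol 2.1 | produced by treatment | study population | No |
| Protocol 2.6, Question 1; SAP 3.0 | any | all study doses | Yes |
| Protocol 2.6, Re 1 | any | fully active dose | Yes |
| SAP 3.3 objectives | serious events not mentioned | not stated | Cannot be answered |

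**Step 2: number exposed to the fully active dose.** Protocol 2.8.1 gives the allocation: "Eight of 12 subjects, or 66.6%, will be assigned to the Fully Active dose condition, and 4 of 12, or 33.3" per cent to the Low Dose condition. Under Protocol 2.8.6, a low-dose participant who consents to Stage 2 enters a stage in which "he or she would receive the Fully Active dose of MDMA". The planned number is therefore 8 if nobody crosses over and 8 + 4 = 12 if all four do. Protocol 2.7 replaces drop-outs, so the actual number can be higher.

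**Step 3: what a zero count leaves open.** The exact (Clopper-Pearson) two-sided 95% upper limit for 0 of n is 1 − 0.025^(1/n).

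- n = 8: 1 − 0.025^(1/8) = 1 − 0.6306 = 36.9%.
- n = 12: 1 − 0.025^(1/12) = 1 − 0.7354 = 26.5%.

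**Step 4: how often a zero count occurs at a given true risk.** The chance is (1 − p)^n. The documents give no expected rate, so p is an assumption, shown over a range.

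| True risk per person | n = 8 | n = 12 |
|---|---|---|
| 5% | 66% | 54% |
| 10% | 43% | 28% |
| 20% | 17% | 7% |
| 30% | 6% | 1% |

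**Step 5: a single event is just as imprecise.** The exact 95% interval is 0.3% to 52.7% for 1 of 8 and 0.2% to 38.5% for 1 of 12.

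**The case against.** The strongest reply is that this is a small pilot stating an expectation, and that the raw material is already planned. Seriousness, relatedness, dose and timing are all collected, so an unrelated hospital stay would appear in the listing as serious and not related. A reader could work out the proportion and the split by relatedness unaided. Protocol 2.1 is a summary, and SAP 3.0 carries Question 1 over without change. Protocol 2.8.3 also admits, for efficacy, that only large effects can be detected. All of this stands. It narrows the gap to an objective, an estimate and an agreed reading, but does not close it, because SAP 3.3 claims to formulate Question 1 and leaves out its subject.

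Three stronger readings are tempting, and the documents do not support them.

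- A reader might infer a formal rule under which zero events confirms safety and one event refutes it. No section states such a rule or ties a decision to it.
- A reader might infer that counts of severe events are meant to answer Question 1. SAP 6.5.3 uses them to study demographic factors, condition and dose, alongside counts of all events, and never presents them as that answer.
- A reader might want a probability that unrelated events alone would overturn Re 1. The documents give no background rate. They also set no collection window common to all full-dose participants: SAP 6.5.3 links follow-up events to the Extended Assessment 1 group, and SAP 6.4.2, Analysis #4, speaks of three participants assessed at 2, 6 and 12 months.

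**Conclusion.** The point holds as one of inconsistent wording and a missing estimate. Protocol 2.1 and Re 1 give opposite answers to the same unrelated serious event, SAP 3.3 drops serious events from the objectives that are meant to express Question 1, and no proportion or interval is planned.

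A zero count would be compatible with a true risk of up to 36.9% (n = 8) or 26.5% (n = 12). These limits need no assumed event rate. They assume only independent participants with a common risk, complete ascertainment, and the stated numbers exposed.

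It would go too far to say that the trial would probably look safe whatever the risk. Zero events is quite likely at a risk of 5% to 10%, but happens in only 6% or 1% of trials at 30%. Nor does the point call for a larger pilot. It is a cheap improvement that changes what may be concluded about the trial's first question.

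**What to change.** Make the change in the SAP and the report. SAP 4.0 describes study conduct mostly in the past tense, and SAP 8.0 says that preliminary outcome data were presented in 2010 and 2011, so rewriting the protocol hypotheses would serve little purpose.

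1. Add serious adverse events to the objectives in SAP 3.3.
2. Answer Question 1 with the proportion of participants who have at least one serious adverse event after a fully active dose: Stage 1 full-dose participants plus Stage 2 crossovers. Use the actual number exposed as denominator, including drop-outs who were replaced.
3. Give this for all causes and, separately, for events judged possibly or probably related, each with an exact 95% interval. This serves both the Re 1 wording and the 2.1 wording.
4. State the collection window.
5. Show the 25 mg period and the Stage 3 sessions at 150 mg separately.
6. State that a zero count does not establish the absolute wording of the hypotheses but only bounds the risk at the exact limit for the actual number exposed (36.9% if that number is 8, 26.5% if it is 12).

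The data fields are already planned in SAP 6.5.3. The cost is one table row, a few sentences, and a safety statement less favourable than the hypotheses suggest.
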